Document Cover Page

Official Title of the Study:

Responsible Fatherhood Opportunities for Reentry & Mobility (ReFORM)

NCT Number: NCT02860988

Date of Document: September 29, 2020

Responsible Fatherhood Opportunities for Reentry & Mobility (ReFORM) Protocol

Background

Mountain Comprehensive Care Center (MCCC) in Prestonsburg, KY was recently awarded a grant from the Administration for Children and Families (ACF) as part of the Responsible Fatherhood Opportunities for Reentry and Mobility (ReFORM) Program to strengthen positive father-child engagement, improve employment and economic mobility opportunities, improve healthy relationships and marriage, and decrease barriers to successful community reentry. MCCC has a physical presence in Floyd, Johnson, Lawrence, Magoffin, Martin and Pike in eastern Kentucky and established relationships with the two targeted detention centers for pre-release services (Floyd County Detention Center and Big Sandy Regional Detention Center).

To address barriers to service participation, grant funding will be used to provide evidence-based services to strengthen parenting skills for fathers who are incarcerated and planning for community re-entry, along with interventions to increase economic mobility and relationships. Individualized, culturally- /gender- competent and comprehensive case management and wraparound services will also foster program participation and success. The project will offer integrated services for fathers who are incarcerated in the targeted area who are incarcerated in Floyd County or Big Sandy facilities. Responsible parenting activities will include skills-based parenting education, dissemination of information regarding good parenting practices, one-on-one counseling regarding parenting issues, and will encourage and seek to facilitate the financial support of participants' children. Economic stability activities will include job readiness workshops, and upon release, linkages with additional job training and educational assistance, job search and placement assistance as well as employment incentives at 30 days of employment. Finally, healthy marriage/relationship activities will include marriage and relationship education, conflict resolution skills training, financial literacy seminars and counseling. Semi-annual parent/child events and annual relationship events will also be available to foster stronger family connections.

Objectives

The ACF award to MCCC primarily supports service enhancement and service delivery. To ensure the effectiveness of the proposed services, MCCC will be contracting with University of Kentucky to perform the evaluation. The evaluation includes two primary components:

- 1) consultation on the collection of ACF required Performance Measures to document program client characteristics, program operations, enrollment and participation, and pre-test/post-test outcome measures; and
- 2) responsibility for the local evaluation which includes a quasi-experimental two group design to examine the effectiveness of targeted services for fathers at MCCC

Study Design

The local evaluation will utilize a quasi-experimental research design including an experimental group (receives MCCC targeted services under the newly funded ACF grant) and a comparison group (incarcerated fathers who do not receive targeted services in a comparable local regional jail). The Kentucky River Regional Jail (KRRJ) is selected as the site for comparison group recruitment because it does not fall in the Mountain Comprehensive Care designated service region, and individuals residing in the KRRJ are comparable in demographics and other key variables of interest.

In the proposed evaluation, eligibility criteria used to select participants for the targeted MCCC grant-funded services in the Floyd County Detention Center and the Big Sandy Regional Detention Center will also be implemented in a comparison jail site. The Kentucky River Regional Jail (KRRJ) located in Hazard, Kentucky is not in the targeted service area for this MCCC project. KRRJ is comparable in size, characteristics of the offender population, and geographic location to the targeted facilities in Floyd County and Big Sandy. Following standardized screening based on grant eligibility criteria, the only anticipated difference between the experimental condition and the comparison condition is the opportunity to receive targeted services based on jail.

Following targeted screening, participants in the experimental (n=250) and comparison groups (n=250) will participate in baseline interviews focused on fatherhood, family relationships, and economic stability indicators, as well as factors which might impact these key outcomes including substance abuse and mental health. All participants in the local evaluation will also complete the post-test assessment at the conclusion of the courses (experimental group) or at a comparable time frame of 12 weeks for the comparison group. All evaluation participants will also be followed 6 months post-release from jail to complete an additional post-test assessment for the targeted instruments.

Study Population

The MCCC estimates that during the first year a minimum of 50 participants will be served accounting for up to a 9-month planning period. It is estimated that 150 participants will be served annually in years 2-5, with a final total of 650 participants over 5 years. Of these participating individuals, 250 will be randomly selected (50 each year of the 5 year project) to be involved in the local evaluation. In addition, 250 comparison group participants will be recruited from a non-treatment site (jail). The 500 total participants recruited for the local evaluation will be incarcerated fathers. Participants for the local evaluation will be identified as eligible fathers who have been tried and convicted as an adult; within 3 to 9 months of release; are low-income; and may be an expectant father, a biological father, an adoptive father or a stepfather or who a person who is acknowledged as a father figure (e.g., grandfather) of a dependent child or young adult child up to 24 years of age, and interested in participation. The target population does not exclude individuals from participants because of age, race, ethnicity, sexual orientation, culture, literacy, disability, or language.

Based on data from the two targeted detention centers, 80% of all inmates are male and approximately 94% are parents. It is also anticipated that offenders will share similar characteristics to the targeted area including race (primarily White), chronic poverty, low educational attainment, high unemployment as well as 90% who have been arrested on alcohol or drug-related charges leading to family instability and separation. This population frequently faces not only the challenge of offender status but also substance use when trying to secure employment. Once enrolled in the evaluation, all participating clients will have access to the targeted ReFORM interventions. The local evaluation will enable analysis to focus on the unique contribution of enhancing parenting and relationship skills as well as job readiness and other employment and economic skills.

Subject Recruitment Methods and Privacy

Recruitment efforts will target two groups of incarcerated fathers:

- 1) those who receive MCCC grant funded services (Floyd County Detention Center; Big Sandy Regional Jail, n=250); and
- 2) those who are incarcerated in jails not in the service delivery region for grant funded services (Kentucky River Regional Jail, n=250).

Participants in the treatment group will be informed about the local evaluation at treatment intake, and will be provided with an overview of the evaluation. If MCCC treatment participants are willing to be in the sampling frame for the local evaluation, they will sign the release of information form with the MCCC treatment coordinator. For the comparison group, the UK Program Coordinator will recruit participants from KRRJ once a month based on a randomized schedule. On each recruitment day, UK research staff will randomly select male offenders serving time in the jail from the daily census sheet to participate in the screening sessions. Jail personnel are not engaged in the research and not involved in the random selection of cases, and they will only providing access to the daily census sheet. UK research staff will randomly select 10-15 male participants residing in the jail on the day of screening. All male inmates will have an equal opportunity of being selected for the local evaluation, including minorities, as long as they are at least 18 years of age and not previously screened for the study.

Comparison group recruitment criteria will be matched to MCCC treatment participants including fathers who have been tried and convicted as an adult; within 3 to 9 months of release; are low-income; and may be an expectant father, a biological father, an adoptive father or a stepfather or a person who is acknowledged as a father figure (e.g., grandfather) of a dependent child or young adult child up to 24 years of age, and interested in participation. It is anticipated that approximately 5 comparison group participants will be recruited into the study each month in order to maintain a manageable number of participants for follow-up interviews.

Advertising

N/A

Informed Consent Process

Names of interested and eligible treatment participants will be shared with the UK research staff after they sign a MCCC release of information. No research/evaluation activities will be initiated with the treatment participants until they meet with the UK research staff and sign informed consent. Comparison group participants who are interested in the study will be asked to participate in the screening session at the jail with the UK research coordinator. Potential participants in both conditions will be provided with informed consent prior to the collection of ANY data.

As part of the informed consent process, potential participants will be assured that:

- (a) Neither participation nor refusal to participate in a protocol will affect their legal parole status (if applicable);
- (b) No individual or identifiable data collected as part of a study protocol will be made available to any criminal justice authority including jail, parole, or community mandated treatment; and
- (c) If potential participants do NOT wish to participate, their parole or other legal status will not be affected. Potential participants who choose NOT to participate in the study protocol will not be identified in their records, and nonparticipation will NOT become a matter of official record in any file.

Informed consent procedures will cover participation in the screener (for the comparison group), baseline interview, and follow-up interviews so that participants are fully aware of all possible study procedures before making a decision about entering the study. Due to the sensitive nature of some of the questions asked in the interviews, confidentiality issues will be stressed during informed consent which will include a description of a federal Certificate of Confidentiality which provides an additional layer of human subject protection. Participants will also be assured that their screening results, study participation, and study data will not be made available to any representative of the criminal justice system. The research coordinator will keep detailed records on the number of interested participants who participate in the screening session and the number of refusals. Screening data will be examined as part of the implementation phase to examine characteristics of participants who enter the study compared to those who are not eligible. Because of the short time frame between baseline and follow-up interviews (approximately 12 weeks), consent procedures will not be repeated at each follow-up interview since no new procedures will be introduced. However, a follow-up script will be reviewed with The participant to remind him of the key elements of informed consent.

Research Procedures

To fulfill the requirements of the ACF funded grant, agency administrators and treatment staff are required to collect standardized performance measures. The evaluation PI will be given access to de-identified data through the ACF mandated nFORM data management system in order to assist the agency with data analysis for quarterly reports on:

- 1) program inputs (recruitment, enrollment, and characteristics of the client population);

- 2) program activities (quality assurance and monitoring, implementation challenges, and referrals to community agencies);
- 3) program outputs (enrollment, timing of client participation, program attendance, and overall program retention); and
- 4) program outcomes (changes in parenting behaviors, economic stability, relationships, personal development and well-being, and overall perceptions of the program).

These data are de-identified and required by the funding agency (ACF) to monitor program operations. This IRB application is focused primarily on the local evaluation. The nFORM data will only be used for the local evaluation with a signed release from the participant.

Potential local evaluation participants receiving targeted services at the Floyd County Detention Center or Big Sandy Regional jail will be asked about their interest in the local evaluation. If the participant is interested, he will be asked to sign a release of information to the evaluation team to access his nFORM information (specifically demographics and intake assessments which will be specified on the release). The UK research staff will work closely with MCCC project staff to identify individuals interested in the local evaluation.

Comparison group screening: Following random selection, the purpose of the screening session is to identify rural men who meet similar criteria as individuals receiving targeted MCCC services. The screening session (estimated 20 minutes) will be conducted between a trained study interviewer and the potential participants either in a face-to-face format or in a group setting, depending on the available jail accommodations. The session will include informed consent and an emphasis on the voluntary nature of study participation. Following consent, participants will be administered the ReFORM screening assessment (under development, will be forwarded for IRB approval prior to implementation). If the screener is administered in a group format, questions will be read aloud to participants and responses will be recorded confidentially on paper copies of the screener. Eligible participants will need to meet all of the specified study criteria to be invited to do a baseline interview.

Data collection: Potential comparison group participants meeting study eligibility criteria will complete a face-to-face baseline interview with the study interviewer the same day of the initial screening session, which is expected to last about 1 hour. Treatment group participants will also complete the required assessment interviews with the research staff after being identified as being interested in the local evaluation. The interviewer will be trained in the study protocol, as well as in jail policies and procedures. Interviews will be conducted in the jail visiting rooms which are large enough to provide a confidential face-to-face interview, and have been used to conduct interviews for other studies with offenders. While jail staff may monitor participant entry and exit into the visitation room, no jail staff will be present for the confidential interviews.

Data collection for the evaluation will include the initial Fatherhood Pre-test for Incarcerated Fathers, followed by an interview with the Evaluation Coordinator (in person, phone, or Wi-Fi audio) at 12 weeks post-intake (or completion of services), and again at 6 months post-release from jail. Participants will receive incentives for their time to complete data collection interviews.

Document Cover Page

Official Title of the Study:

Responsible Fatherhood Opportunities for Reentry & Mobility (ReFORM)

NCT Number: NCT02860988

Date of Document: January 15, 2020

STATISTICAL ANALYSIS PLAN

Analytic Sample:

The primary analysis sample will be used to address each primary research question. This sample consists of individuals with both baseline and six-month follow-up data.

Baseline equivalence between the intervention and comparison groups will be investigated for all demographic, criminal history, and other background characteristics. The equivalency of all primary and secondary outcome measures will also be investigated. Continuous variables will be compared using parametric (*t*-tests) and nonparametric (Wilcoxon rank-sum test) methods, whereas categorical variables will be compared using chi-square and Fisher's exact tests. All baseline equivalency measures will be performed with two-tail tests using an α of .05. Situations involving significant between group differences will be further characterized with effect sizes, using Hedges' *g* for the continuous outcomes and the Cox index for categorical outcomes. Any variables meeting the criteria of $p < .05$ will be discussed with the ETTA and considered for use as control variables for the analysis of primary and secondary outcomes. Other methods, for example, propensity score weights, will also be discussed if significant imbalance is observed.

Because the majority of services are provided in a jail setting, and the intervention and counterfactual samples are recruited from different institutions, the potential for condition crossover is not a concern.

Analytic Approach:

SPSS version 26 will be used to perform all analysis and data management. All parameters meeting the criteria $p < .05$, two-tailed, will be considered statistically significant. As the number of primary outcome measures is delimited, α corrections for multiple comparisons are not necessary. There will be no differences between how primary and secondary research questions are analyzed.

The exact specification of the analytic model will depend on the nature of the outcome variable: continuous vs binary. In order to account for the longitudinal nature of the data, hierarchical linear models and hierarchical generalized linear models will be used to analyze continuous and binary outcomes, respectively. These methods allow for the nested structure of the data, where measurement occasion (level one) is nested within individual (level two), to be accounted for analytically.

Due to the quasi-experimental nature of the study design, simply controlling for baseline levels of the outcome of interest could be misleading since participants were not randomly assigned to the intervention vs counterfactual condition, and therefore have the potential to be significantly different at baseline. One method of accounting for these potential differences is to use a difference in differences model. Rather than controlling for baseline levels, the baseline value is instead considered as an additional timepoint and modeled as a difference score. The outcome is modeled as follows:

$$Y_i = \beta_0 + \beta_1 T_i + \beta_2 t_i + \beta_3 (T_i \times t_i) + \varepsilon_i$$

Where T is a dummy variable that takes on the value of 1 if individual i is in the intervention group and 0 otherwise, and t is a dummy variable that takes on the value of 1 for data from the six-month follow-up and 0 otherwise. The model terms can be interpreted as such:

β_0 – outcome mean for counterfactual condition at baseline

β_1 – difference in outcome mean between intervention and counterfactual at baseline

β_2 – change in outcome mean from baseline to six-month follow-up for counterfactual condition

β_3 – difference in the change in outcome means between intervention and counterfactual condition

As a result, the parameter of interest for determining an intervention difference is β_3 .

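### Significance at .05 is the only stated trigger for sizing or acting on a baseline gap between the jails, so observed gaps up to about 0.18 SD at 250 per group get no effect size

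*SAP*

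**What the plan says.** The SAP, under Analytic Sample, investigates equivalence of background characteristics and of baseline outcomes. It specifies that "All baseline equivalency measures will be performed with two-tail tests using an α of .05". The tests are t and Wilcoxon for continuous variables, and chi-square and Fisher for categorical ones.

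Three consequences depend on the result:

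- **Effect size.** "Situations involving significant between group differences will be further characterized with effect sizes" (Hedges' g or the Cox index).
- **Control variables.** Variables with p < .05 "will be discussed with the ETTA and considered for use as control variables".
- **Weighting.** Other methods, such as "propensity score weights, will also be discussed if significant imbalance is observed".

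Neither document gives an effect-size limit or equivalence margin. Condition is fixed by jail, and the Protocol (Study Design) holds that "the only anticipated difference between the experimental condition and the comparison condition is the opportunity to receive targeted services based on jail". The SAP (Analytic Approach) nevertheless accepts that the groups may differ at baseline, and uses a difference-in-differences model without covariates for that reason.

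**The concern.** A test of difference that fails to reject zero does not show that a difference is small. The gap that escapes notice is set by the number of men, not by how much imbalance would matter. Gaps just short of significance are the ones whose size a reader most needs, and the SAP assigns them no effect size and no route to adjustment.

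This matters more here than in a randomised trial. The two groups come from different jails and by different routes. Intervention men are service clients who agree to enter the sampling frame, while comparison men are drawn at random from a daily census sheet (Protocol, Subject Recruitment Methods and Privacy). The baseline check is the plan's means of examining whether services are the only difference. If a characteristic differs between jails and also predicts change over time, β_3 is biased by the gap times the slope of change on that characteristic.

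**Working it through.** **Inputs from the documents.** Two-sided α = .05 (SAP, Analytic Sample) and 250 men per group (Protocol, Study Design). No attrition rate, power calculation or equivalence margin is stated, so there is no planned figure to reproduce. Sizes below 250 are assumptions that show the range.

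**1. Smallest gap that reaches p < .05.** In SD units this is t(.975, 2n−2) × √(2/n). At n = 250 it is 1.965 × √(2/250) = 1.965 × 0.0894 = 0.176.

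**2. Chance that a true 0.20 SD gap is non-significant.** This uses the noncentral t with noncentrality 0.20 × √(n/2), which is 2.236 at n = 250.

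| n per group | Critical gap (SD) | True 0.20 SD gap missed |
|---|---|---|
| 250 (planned) | 0.176 | 39% |
| 180 (assumed) | 0.207 | 53% |
| 175 (assumed) | 0.210 | 54% |
| 125 (assumed) | 0.249 | 65% |

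The lower rows apply only if the tests are run on men with both baseline and six-month data.

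**3. Binary variable, 50% in one group.** The pooled two-proportion test at n = 250 needs a difference of about 8.7 points. In whole men, the first significant result (uncorrected chi-square) is 147 against 125 of 250. That is 22/250 = 8.8 points, with Cox index ln(147/103)/1.65 = 0.22. At an assumed 180 it is 109 against 90, which is 10.6 points and Cox index 0.26.

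**4. Effect on β_3 when the gap goes unflagged.** Illustrative assumptions: true gap 0.20 SD, change rising 0.3 SD per SD of the characteristic, baseline–follow-up correlation 0.5, no programme effect.

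- SE(β_3) = √(4(1−0.5)/n) = 0.0894 at 250 and 0.1054 at 180.
- The observed gap was simulated as normal with mean 0.20 and variance 2/n, feeding into β_3 at slope 0.3. Only trials in which the characteristic was non-significant were kept.
- In those trials the mean observed gap is 0.11 SD (n = 250) or 0.12 SD (n = 180), so the mean bias in β_3 is 0.3 × 0.11 = 0.033 or 0.3 × 0.12 = 0.036 SD.
- The two-sided 5% error rate becomes 5.9% at 250 and 5.7% at 180.
- With two independent characteristics acting in the same direction and both unflagged, it is about 10% at 250 and 9% at 180. Both go unflagged in 0.393² = 15% of trials at 250 and 0.527² = 28% at 180.

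**5. False flags under true balance.** With an assumed 30 baseline variables, p < .05 flags 30 × 0.05 = 1.5 by chance. A limit of |g| > 0.10 flags 2(1 − Φ(0.10/0.0894)) = 26% at 250 and 34% at 180, or about 8 to 10 of the 30.

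**The case against.** Four points on the other side carry weight.

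- **The SAP never says that a non-significant variable is equivalent.** It says equivalence will be investigated and states no pass rule. This stands. A reader might infer that non-significance will be reported as equivalence, but the text supports only the narrower statement that p < .05 is the sole trigger for measuring or acting.
- **The model does not rely on equal baselines.** A stable gap in an outcome cancels from β_3, and β_1 estimates that gap in raw units whatever its p-value. This stands for outcomes. It does not cover a background characteristic that predicts change, because the stated model has no covariates and such a variable with p ≥ .05 is not considered for control.
- **Attrition loosening the check is conditional.** The tests are described directly after the completer sample is defined, but the SAP does not say which men are tested. If all 500 are tested, the limit stays at 0.176 SD.
- **An effect-size limit has its own costs.** A tight limit flags many variables by chance. A cutoff on the point estimate also depends on sample size: a true 0.15 SD gap falls below 0.10 about 29-31% of the time. This is a reason to choose the limit with care and to show confidence intervals. It does not justify keeping the p-value trigger.

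**Conclusion.** The concern holds in a limited form. At the planned size, an observed gap up to 0.176 SD receives no effect size and no stated consideration, and a true 0.20 SD gap escapes 39% of the time. These two figures need only α and n from the documents. The looser limits of 0.21 and 0.25 SD rest on assumed attrition and on the check being run on completers.

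The demonstrated effect on β_3 is modest: an error rate of about 6% when one gap goes unflagged and 9-10% when two in the same direction do, under the assumed gap, slope and correlation. A reader might infer something larger by putting the full 0.20 × 0.3 = 0.06 SD bias into every trial, which gives 9-10% for one variable and 21-27% for two. Those figures average over trials in which the SAP's own test flags the gap, 61% of them at 250 per group for one variable. They would describe the plan only if flagged variables were never adjusted for, and the SAP says they will be considered.

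The primary model survives. The weakness is in the evidence offered that the jails are comparable, and it should be corrected before analysis.

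**What to change.** Amend the SAP's Analytic Sample section as follows:

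- Calculate and report Hedges' g (continuous) or the Cox index (binary, with each category against the rest for multi-category variables), with a 95% confidence interval, for every baseline characteristic and every baseline primary and secondary outcome.
- Do this in all enrolled men and again in the primary analysis sample, which also settles which sample is tested.
- Fix an absolute effect-size limit in advance with the ETTA, and let that limit, not p < .05, trigger consideration of control variables or weighting. A limit of 0.10 is an example only; the documents give no basis for a particular value.
- The p-values may still be listed, but should not decide.

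The metrics are already named in the SAP and no new data are needed. The cost is revised wording, one larger table, and more variables to discuss if the limit is tight: at 0.10, about 26% of truly balanced variables at 250 per group.

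### The SAP's model has no level above the individual, so if intervention men are taught in groups and group-mates change alike, the standard error of β_3 is too small

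*SAP*

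**What the plan says.** The SAP (Analytic Approach) uses hierarchical linear models for continuous outcomes and their generalized counterpart for binary ones. The reason given is that they handle nesting, which is defined as a structure "where measurement occasion (level one) is nested within individual (level two), to be accounted for analytically". The displayed equation carries a single error term and no term for course, cohort, facilitator or jail. Neither document mentions a robust or clustered standard error. The SAP states that "the parameter of interest for determining an intervention difference is β_3", the group-by-time interaction. Any parameter with p < .05, "two-tailed, will be considered statistically significant", and no multiplicity correction is made.

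The protocol describes the programme largely in terms that suggest classes. In Background, "Economic stability activities will include job readiness workshops", and the relationship component covers "marriage and relationship education, conflict resolution skills training, financial literacy seminars and counseling". In Study Design, the first post-test for the intervention arm falls "at the conclusion of the courses (experimental group"). The same Background section also offers one-to-one parenting counselling and individualized case management. Comparison men come from a jail where the targeted services are not offered.

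On numbers, "participants in the experimental (n=250) and comparison groups (n=250) will participate in baseline interviews". Study Population expects 650 men to be served over five years, of whom 250 are randomly selected for the evaluation, 50 in each year.

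**The concern.** If intervention men sit in the same class, they share an instructor, a set of peers and a period of delivery, and their changes from baseline may be correlated. Comparison men receive none of the targeted services, so this source of correlation exists in one arm only: a partially nested design.

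The planned model cannot absorb it. With one baseline and one six-month value per man, β_3 is the difference between arms in mean change. A random intercept per man enters both of his measurements and cancels from his change score. It accounts for stable differences between men, not for a shift that classmates share.

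At stake is the precision claimed for β_3. With positive within-group correlation of change, the confidence interval would be too narrow and a true null would be rejected more often than the stated 5%. The estimate itself would not be shifted.

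**Working it through.** The documents give no power calculation, ICC or class size, so there is no figure of the plan's own to reproduce. The check asks how far the standard error would be off under stated assumptions.

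**Inputs from the documents**
- Arms of 250 and 250 (Protocol, Study Design).
- Men served: 50 + 4 × 150 = 650. Evaluated: 5 × 50 = 250. Share evaluated: 250/650 = 38% (Protocol, Study Population).
- Two-sided α of .05 (SAP, Analytic Approach).

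**Assumptions**
- Classes of 10 to 15 men. At 38% evaluated, the number of evaluated men per class is m = 10 × 0.385 = 3.85 to 15 × 0.385 = 5.77, about 4 to 6.
- ICC of the change score, ρ, of 0.05 to 0.10, with 0.02 and 0 as lower cases.
- Continuous outcome, complete pairs, equal variance of change in the two arms. For binary outcomes the algebra is only approximate.

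**Formulas**
- Design effect in the intervention arm: DE = 1 + (m − 1)ρ. In the comparison arm it is 1.
- True SE / model SE = √[(DE + 1)/2] for equal arms.
- Actual two-sided error = 2 × P(Z > 1.96/ratio).

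Example: m = 5.77 and ρ = 0.10 give DE = 1 + 4.77 × 0.10 = 1.477; ratio = √(2.477/2) = 1.113; 1.96/1.113 = 1.761; error = 7.8%.

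| m | ρ | DE | True SE / model SE | Model SE too small by | Two-sided error |
|---|---|---|---|---|---|
| any | 0 | 1.00 | 1.000 | 0% | 5.0% |
| 3.85 | 0.02 | 1.06 | 1.014 | 1.4% | 5.3% |
| 5.77 | 0.02 | 1.10 | 1.024 | 2.3% | 5.6% |
| 3.85 | 0.05 | 1.14 | 1.035 | 3.4% | 5.8% |
| 3.85 | 0.10 | 1.28 | 1.069 | 6.4% | 6.7% |
| 5.77 | 0.05 | 1.24 | 1.058 | 5.5% | 6.4% |
| 5.77 | 0.10 | 1.48 | 1.113 | 10.1% | 7.8% |

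The fifth column is 1 − 1/ratio. It is slightly smaller than the factor by which the interval would have to widen.

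**Simulation.** With 250 per arm and 20,000 simulated trials per setting, the error was 5.0% at m = 5, ρ = 0; 6.0% at m = 5, ρ = 0.05; and 7.3% at m = 5, ρ = 0.10. The formula gives 5.0%, 6.2% and 7.4%.

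**Uneven sampling by year.** The 38% is an average. If year 1 served only its minimum of 50 men, all of them would be evaluated, against 50 of 150 in later years. Year 1 is one fifth of the arm. Weighting by year, with 1 + (M − 1) × 49/149 evaluated men per class of size M in years 2 to 5, gives m = 0.2 × 10 + 0.8 × 3.96 = 5.2 for classes of 10 and 0.2 × 15 + 0.8 × 5.60 = 7.5 for classes of 15. At ρ = 0.05 to 0.10 the error then runs from 6.2% (m = 5.2, ρ = 0.05) to 8.9% (m = 7.5, ρ = 0.10).

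**The case against.** The strongest reply is that group delivery is inferred. Neither document says that sessions are held in groups, how large they are, or that men start together. Some services are one-to-one. Under Research Procedures the second interview is timed to each man's own 12 weeks or completion of services, which also fits rolling entry. This stands, and it is why the point is conditional: with no shared group, or one evaluated man per group, nothing changes.

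The ICC may also be low. The analysed outcome is six months after release, when men no longer share a class, and the analysis keeps only men with six-month data, so any loss to follow-up thins the groups further. This also stands. At ICC 0.02 the effect is negligible.

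Two stronger readings are tempting but unsupported. A reader might infer that the error favours declaring the programme effective. It does not: an understated standard error leaves β_3 where it is, and under a two-tailed test 5.8% to 7.8% means 2.9% to 3.9% in each direction. A reader might also take whole classes of 10 to 15 as evaluated throughout, which at ICC 0.05 to 0.10 would put the error at 7.7% to 13.3% and make the model's standard error 10% to 23% too small. The planned sampling of 50 of about 150 men a year rules that out for years 2 to 5. It could hold at most for year 1.

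Finally, in a comparison of two intervention jails with one other jail, differences between jails may matter more than this. That may be so, and a course level would not help with it, but it gives no reason to leave the standard error wrong.

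**Conclusion.** The point holds in conditional form. The SAP's model has no place for correlation between men taught together, and the protocol's description of the programme makes such correlation plausible in the intervention arm. If it exists, the standard error of β_3 is too small.

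Under the assumed class sizes and an ICC of change of 0.05 to 0.10, the true standard error is 1.03 to 1.11 times the model's (the model's is about 3% to 10% too small), and the two-sided error is about 5.8% to 7.8%. The size rests on class size and ICC, neither of which is in the documents. This is a modest defect with an inexpensive remedy: it should be corrected, but it does not by itself undermine the study.

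**What to change.** Amend the SAP so that the standard error of β_3 is clustered on each intervention man's main course group, with each comparison man as his own unit. An equivalent choice is a random cohort effect on change that applies only when T = 1. With 650 men served in classes of 10 to 15 there would be about 43 to 65 groups (650/15 and 650/10), enough for either approach.

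Define the group by what was delivered. Facility and start date alone may not identify it if parenting, employment and relationship sessions draw different men. Two sources are available:
- Programme attendance and timing records, which the protocol lists among the reported programme outputs. The release that men sign is specified for demographics and intake assessments, so it would need extending.
- The course and start date, recorded at the 12-week interview.

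Men served only individually, or through rolling entry with no shared group, count as their own unit. The SAP should also state how sessions are delivered.

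The cost is one identifier per intervention man, possibly a revised release, and a sentence or two in the SAP. The confidence interval widens by about 3% to 11% under the assumptions above and hardly at all if the ICC is near zero. The change does nothing about confounding by jail, which needs separate treatment.
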